## **8.3 Second Vaccination Visit**

### **8.3.1 Visit 06, Study Day 29±3, Second Vaccination Clinic Visit**

- Obtain interim medical history, including an assessment for new medical conditions by interview of subjects and note any changes since the previous clinic or phone visit.
- Review eligibility criteria\*  
\*Except for: Inclusion Criteria 1, 2, 5, 6; and Exclusion Criteria 3.
- Review [section 9.5.2](#) to be sure subject has not met a Halting Criteria for 2nd vaccination.

- Collect urine for a urine pregnancy test, which must be performed within 24 hours prior to study vaccine administration on all female subjects of childbearing potential. Results must be known and negative prior to receipt of study vaccine.
- Review medical history to assure continued eligibility.
- Ask about febrile/rash illness. If the subject reports history of AFI/ARI within the past 14 days, conduct a febrile/rash illness Assessment and sample collection as per [Section 8.7](#).
- Collect information on all concomitant medications taken since last visit and record on the appropriate case report form.
- Perform a targeted physical examination, if indicated based on review of complete medical history.
- Obtain vital signs including oral temperature, blood pressure, and pulse.
- Collect blood samples for humoral immunity, CPT tubes and a Paxgene tube.
- Do a pre-administration reactogenicity assessment prior to the second study vaccination to establish baseline. Subjects will receive a single dose of study vaccine via IM injection into the deltoid muscle of the preferred arm.
- Observe in the clinic for at least 30 minutes after the vaccination to monitor for any acute reactions and evaluate the vaccination site and assess reactogenicity.
- Assess for unsolicited AEs, SAEs, AESIs, and new onset chronic medical conditions and record on the appropriate case report form.
- Instruct subject about importance of reactogenicity monitoring and remind about the Day 2 clinic follow-up visit.
- Provide subject with a memory aid, thermometer, and ruler for recording daily maximum oral temperature and systemic and local AEs beginning with the day of vaccination and continuing for the next 7 days. Subjects will be encouraged to take their temperature around the same time each day and also if they feel feverish, beginning with the day of vaccination. Subjects will be instructed on how to use the memory aid and how to rate any adverse events. Subjects will be asked to bring their Memory Aid with them at their next study visit.

### **8.3.2 Visit 07, Study Day 30, Day 2 Clinic Visit after Second Vaccination.**

- Obtain interim medical history, including an assessment for new medical conditions by interview of subjects and note any changes since the previous clinic or phone visit.
- Ask about febrile/rash illness. If the subject reports history of AFI/ARI within the past 14 days, conduct a febrile/rash illness Assessment and sample collection as per [Section 8.7](#).
- Collect information on all concomitant medications taken since last visit and record on the appropriate case report form.
- Perform a targeted physical examination, if indicated based on review of complete medical history.
- Obtain vital signs including oral temperature, blood pressure, and pulse.
- Review the Memory Aid with the subject.
- Examine vaccination site for local reactions.
- Collect blood samples for a CPT tube and a Paxgene tube.
- Assess for unsolicited AE, SAEs, AESIs, and new onset chronic medical conditions and record on the appropriate case report form.

### **8.3.3 Visit 08, Study Day 32 +1; Day 4 Phone Visit after Second Vaccination**

- Obtain interim medical history, including an assessment for new medical conditions by interviewing subject by phone. Record any changes since the previous clinic or phone visit.
- Ask about febrile/rash illness. If the subject reports history of AFI/ARI within the past 14 days, ask the subject to come in for a febrile/rash illness Assessment and sample collection as per [Section 8.7](#).
- Collect information on all concomitant medications taken since last visit and record on the appropriate case report form.
- Ask subject about information that they have collected since Day 1 on their paper Memory Aid. If subject has an AE that they are concerned about, encourage them to come into the study clinic to be evaluated.

- Ask about unsolicited AEs, SAEs, AESIs, and new onset chronic medical conditions and record on the appropriate case report form.

#### **8.3.4 Visit 09, Study Day 36±1, Day 8 Clinic Visit after Second Vaccination**

- Obtain interim medical history, including an assessment for new medical conditions by interview of subjects and note any changes since the previous clinic or phone visit.
- Ask about febrile/rash illness. If the subject reports history of AFI/ARI within the past 14 days, conduct a febrile/rash illness Assessment and sample collection as per [Section 8.7](#).
- Collect information on all concomitant medications taken since last visit and record on the appropriate case report form.
- Perform a targeted physical examination, if indicated based on review of complete medical history.
- Obtain vital signs including oral temperature, blood pressure, and pulse.
- Review the Memory Aid with the subject.
- Examine vaccination site for local reactions.
- Collect blood samples for CPT tubes and a Paxgene tube.
- Collect venous blood for safety laboratory tests including WBC, hemoglobin, hematocrit, platelets, ALT, AST, total bilirubin, BUN, creatinine.
- Collect urine for urine dipstick for glucose and protein.
- Assess for unsolicited AE, SAEs, AESIs, and new onset chronic medical conditions and record on the appropriate case report form.

#### **8.3.5 Visit 10, Study Day 43±2, Day 15 Clinic Visit after Second Vaccination**

- Obtain interim medical history, including an assessment for new medical conditions by interview of subjects and note any changes since the previous clinic or phone visit.
- Ask about febrile/rash illness. If the subject reports history of AFI/ARI within the past 14 days, conduct a febrile/rash illness Assessment and sample collection as per [Section 8.7](#).

- Collect information on all concomitant medications taken since last visit and record on the appropriate case report form.
- Perform a targeted physical examination, if indicated based on review of complete medical history.
- Obtain vital signs including oral temperature, blood pressure, and pulse.
- Examine vaccination site for local reactions.
- Collect venous blood for safety laboratory tests including WBC, hemoglobin, hematocrit, platelets, ALT, AST, total bilirubin, BUN, creatinine.
- Collect urine for urine dipstick for glucose and protein as part of the safety laboratory tests.
- Collect blood samples for humoral immunity, CPT tubes and a Paxgene tube.
- Assess for unsolicited AE, SAEs, AESIs, and new onset chronic medical conditions and record on the appropriate case report form.

#### **8.3.6 Visit 11, Study Day 57±3, Day 29 Clinic Visit after Second Vaccination**

- Obtain interim medical history, including an assessment for new medical conditions by interview of subjects and note any changes since the previous clinic or phone visit.
- Ask about febrile/rash illness. If the subject reports history of AFI/ARI within the past 14 days, conduct a febrile/rash illness Assessment and sample collection as per [Section 8.7](#).
- All concomitant medications will be recorded on the appropriate case report form.
- A targeted physical examination will be performed, if indicated based on review of complete medical history.
- Obtain vital signs including oral temperature, blood pressure, and pulse.
- Examine vaccination site for local reactions.
- A urine pregnancy test must be performed on all female subjects of childbearing potential.

- Collect blood samples for humoral immunity and CPT tubes.
- Any unsolicited AEs, SAEs, AESIs, and new onset chronic medical conditions will be assessed and recorded on the appropriate case report form.

### **8.3.7 Visit 12, Study Day 107±14, Day 79 (2.5 Month) Phone Visit after Second Vaccination**

- Contact subjects by phone to ask for any updates on contact information including email address and phone number.
- Obtain interim medical history, including an assessment for new medical conditions by interview of subjects and note any changes since the previous clinic or phone visit.
- Ask about febrile/rash illness. If the subject reports history of AFI/ARI within the past 14 days, ask the subject to come in for a febrile/rash illness Assessment and sample collection as per [Section 8.7](#).
- Any unsolicited SAEs, AESIs, and new onset chronic medical conditions will be assessed and recorded on the appropriate case report form.

### **8.3.8 Visit 13, Study Day 157±14, Day 129 (4.5 months) Phone Visit after Second Vaccination**

- Contact subjects by phone to ask for any updates on contact information including email address and phone number.
- Obtain interim medical history, including an assessment for new medical conditions by interview of subjects and note any changes since the previous clinic or phone visit.
- Ask about febrile/rash illness. If the subject reports history of AFI/ARI within the past 14 days, as the subject to come in for a febrile/rash illness Assessment and sample collection as per [Section 8.7](#).
- Ask about unsolicited SAEs, AESIs, and new onset chronic medical conditions and record on the appropriate case report form.

### **8.3.9 Visit 14, Study Day 209±14, Day 181 (6 Month) Clinic Visit after Second Vaccination**

- Obtain interim medical history, including an assessment for new medical conditions by interview of subjects and note any changes since the previous clinic or phone visit.
- Ask about febrile/rash illness. If the subject reports history of AFI/ARI within the past 14 days, conduct a febrile/rash illness Assessment and sample collection as per [Section 8.7](#).
- A targeted physical examination will be performed, if indicated based on review of complete medical history.
- Collect blood samples for humoral immunity and CPT tubes.
- Any unsolicited SAEs, AESIs, and new onset chronic medical conditions will be assessed and recorded on the appropriate case report form.

### **8.3.10 Visit 15, Study Day 268 ±14, Day 240 (8 months) Phone visit after 2nd vaccination.**

- Contact subjects by phone to ask for any updates on contact information including email address and phone number.
- Obtain interim medical history, including an assessment for new medical conditions by interview of subjects and note any changes since the previous clinic or phone visit.
- Ask about febrile/rash illness. If the subject reports history of AFI/ARI within the past 14 days, ask the subject to come in for a febrile/rash illness Assessment and sample collection as per [Section 8.7](#).
- Ask about unsolicited SAEs, AESIs, and new onset chronic medical conditions and record on the appropriate case report form.

### **8.3.11 Visit 16, Study Day 328±14, Day 300 (10 Months) Phone Call after Second Vaccination**

- Contact subjects by phone to ask for any updates on contact information including email address and phone number.

- Obtain interim medical history, including an assessment for new medical conditions by interview of subjects and note any changes since the previous clinic or phone visit.
- Ask about febrile/rash illness. If the subject reports history of AFI/ARI within the past 14 days, ask the subject to come in for a febrile/rash illness Assessment and sample collection as per [Section 8.7](#).
- Ask about unsolicited SAEs and AESIs and new onset chronic medical conditions and record on the appropriate case report form.

#### **8.3.12 Visit 17, Study Day 388±14, Day 360 (12 months) Clinic Visit Following Second Vaccination**

- Obtain interim medical history, including an assessment for new medical conditions by interview of subjects and note any changes since the previous clinic or phone visit.
- Ask about febrile/rash illness. If the subject reports history of AFI/ARI within the past 14 days, conduct a febrile/rash illness Assessment and sample collection as per [Section 8.7](#).
- A targeted physical examination will be performed, if indicated based on review of complete medical history.
- Collect blood samples for humoral immunity and CPT tubes.
- Any unsolicited SAEs, AESIs, and new onset chronic medical conditions will be assessed and recorded on the appropriate case report form.

#### **8.3.13 Visit 18, Study Day 448±14, Day 420 (14 months) Phone Call following Second Vaccination.**

- Contact subjects by phone to ask for any updates on contact information including email address and phone number.
- Obtain interim medical history, including an assessment for new medical conditions by interview of subjects and note any changes since the previous clinic or phone visit.
- Ask about febrile/rash illness. If the subject reports history of AFI/ARI within the past 14 days, ask the subject to come in for a febrile/rash illness Assessment and sample collection as per [Section 8.7](#).

- Ask about unsolicited SAEs, AESIs, and new onset chronic medical conditions and record on the appropriate case report form.

#### **8.3.14 Visit 19, Study Day 508+14, Day 480 (16 months) Phone Call following Second Vaccination.**

- Contact subjects by phone to ask for any updates on contact information including email address and phone number.
- Obtain interim medical history, including an assessment for new medical conditions by interview of subjects and note any changes since the previous clinic or phone visit.
- Ask about febrile/rash illness. If the subject reports history of AFI/ARI within the past 14 days, ask the subject to come in for a febrile/rash illness Assessment and sample collection as per [Section 8.7](#).
- Ask about unsolicited SAEs, AESIs, and new onset chronic medical conditions and record on the appropriate case report form.

#### **8.3.15 Visit 20, Study Day 569+14, Day 541 (18 months) Clinic Visit following Second Vaccination.**

- Obtain interim medical history, including an assessment for new medical conditions by interview of subjects and note any changes since the previous clinic or phone visit.
- Ask about febrile/rash illness. If the subject reports history of AFI/ARI within the past 14 days, conduct a febrile/rash illness assessment and sample collection as per [Section 8.7](#).
- A targeted physical examination will be performed, if indicated based on review of complete medical history.
- Collect blood samples for humoral immunity and CPT tubes.
- Any unsolicited SAEs, AESIs, and new onset chronic medical conditions will be assessed and recorded on the appropriate case report form.

### **8.3.16 Visit 21, Study Day 629±14, Day 601 (20 months) Phone Visit following Second Vaccination.**

- Contact subjects by phone to ask for any updates on contact information including email address and phone number.
- Obtain interim medical history, including an assessment for new medical conditions by interview of subjects and note any changes since the previous clinic or phone visit.
- Ask about febrile/rash illness. If the subject reports history of AFI/ARI within the past 14 days, ask the subject to come in for a febrile/rash illness assessment and sample collection as per [Section 8.7](#).
- Ask about unsolicited SAEs, AESIs, and new onset chronic medical conditions and record on the appropriate case report form.

### **8.3.17 Visit 22, Study Day 689±14, Day 661 (22 months) Phone Visit following Second Vaccination.**

- Contact subjects by phone to ask for any updates on contact information including email address and phone number.
- Obtain interim medical history, including an assessment for new medical conditions by interview of subjects and note any changes since the previous clinic or phone visit.
- Ask about febrile/rash illness. If the subject reports history of AFI/ARI within the past 14 days, ask the subject to come in for a febrile/rash illness assessment and sample collection as per [Section 8.7](#).
- Ask about unsolicited SAEs, AESIs, and new onset chronic medical conditions and record on the appropriate case report form.

## **8.4 Final Study Visit**

### **8.4.1 Visit 23, Study Day 750±14, Day 722 (24 months) Clinic Visit Following Second Vaccination**

- Obtain interim medical history, including an assessment for new medical conditions by interview of subjects and note any changes since the previous clinic or phone visit.

- Ask about febrile/rash illness. If the subject reports history of AFI/ARI within the past 14 days, conduct a febrile/rash illness assessment and sample collection as per [Section 8.7](#).
- A targeted physical examination will be performed, if indicated based on review of complete medical history.
- Collect blood samples for humoral immunity and CPT tubes.
- Any unsolicited SAEs, AESIs, and new onset chronic medical conditions will be assessed and recorded on the appropriate case report form.

**Table 2: Blood Volume Table**

Study Visit	V00	V01	V02	V04	V05	V06	V07	V09	V10	V11	V14	V17	V20	V23
Study Day and Window	Screen D -28 to D -1	D1	D2	D8 ±1	D15 ±1	D29 ±3	D30	D36 ±1	D43 ±2	D57 ±3	D209 ±14	D388 ± 14	D569±1 4	D750±1 4
Study Day Post Second Study Vaccination		Vac # 1				Vac # 2	D2	D8±1	D15± 2	D29± 3	D181±1 4	D360 ±14	D541±1 4	D722±1 4
Blood Volume (in mL)														
Baseline Flavivirus serology	9													
Screening and Safety Clinical Laboratory Tests	22			10	10			10	10					
Serum for Humoral Immunity	0	27	0	0	27	27	0	0	27	27	27	27	27	27
CPT tubes for Immunity and systems biology	0	40	8	40	40	40	8	40	40	40	40	40	40	40
Paxgene tubes for Systems Biology	0	2.5	2.5	2.5	2.5	2.5	2.5	2.5	2.5					
Daily Total Blood Volume	31	69.5	10.5	52.5	79.5	69.5	10.5	52.5	79.5	67	67	67	67	67
Cumulative Total Blood Volume	31	100.5	111	163. 5	243	312.5	323	375.5	455	522	589	656	723	790

## 8.5 Early Termination Visit (if needed)

The following activities will be performed at the early termination visit for subjects who withdraw, or are withdrawn or terminated from this study:

- Obtain interim medical history, including an assessment for new medical conditions by interview of subjects and note any changes since the previous clinic visit or phone call.
- Ask about febrile/rash illness. If the subject reports history of febrile illness and either non-purulent conjunctivitis or arthralgia within the past 14 days, conduct a febrile/rash illness Assessment and sample collection as per [Section 8.7](#).
- Record concomitant medications on the appropriate case report form if  $\leq$  Day 29 after last study vaccination.
- Obtain vital signs including oral temperature, blood pressure, and pulse if visit occurs on or before Day 57.
- Perform a targeted physical examination, if indicated based on review of complete medical history.
- Examine vaccination site for local reactions if visit occurs  $\leq$  28 days after first or 2nd vaccination.
- Review memory aid if visit occurs  $\leq$  8 days after 1st or 2nd vaccination.
- Obtain labs (safety, immunity (cellular and humoral) and systems biology) appropriate to that visit if visit occurs within window of a regular study visit.
- Collect urine for urine dipstick for glucose and protein if indicated as part of the safety laboratory tests.
- Assess for AEs if occurs on or prior to Day 57.
- Assess for unsolicited SAEs and AESIs and new onset chronic medical conditions and record on the appropriate case report form.
- Obtain urine for pregnancy if subject is a female of child bearing age and visit occurs on or before Day 57.

---

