### **7.1.3 Febrile or Rash Illness Assessment**

For this study, AFI will be defined as grade 1 or higher fever lasting at least two consecutive days and accompanied by any one of:

- 1) new rash not limited to vaccination site,
- 2) arthralgia, or

- 3) nonpurulent conjunctivitis.

ARI will be defined as new rash not limited to vaccination site.

Subjects will be informed during the screening period about the long term surveillance and follow-up of all AFI and ARI during the study. They will be told to report all AFI and ARI to the study site within 3 days of symptom onset and come in for an assessment within 14 days (as soon as possible).

Subjects will also be asked at every follow-up visit after signing the ICF about AFI or ARI since the last visit.

The following assessment will be completed if a report of AFI or ARI is made during a regular or unscheduled visit. If it occurs during a regular visit, all procedures outlined in [Section 8](#) appropriate for that day should be performed as well. The febrile/rash illness visit procedures include:

- Obtain interim medical history with focus on collecting signs and symptoms consistent with arboviral disease including duration and severity, and history of medical care received.
- Obtain interim travel history for any trips outside of Puerto Rico since the previous clinic visit or phone call, and record information including travel destination and duration of time at destination on the appropriate form.
- Record concomitant medications taken from time of onset of illness on the appropriate case report form.
- Obtain vital signs including oral temperature, blood pressure, and pulse.
- Perform a targeted physical examination.
- Collect blood (whole blood and serum) and urine to evaluate for possible ZIKV, DENV, and chikungunya virus (CHIKV) infection with qRT-PCR and for other evidence of acute ZIKV and DENV infection.
- Assess for unsolicited AEs, SAEs and AESIs and new onset chronic medical conditions and record on the appropriate case report form.

If the subject reports history of AFI/ARI which began more than 14 days ago, the subject will be asked questions about their illness including onset date, signs and symptoms, severity and

---

duration of symptoms, medications used, healthcare seeking behavior, and travel history and this information will be recorded.

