## 8.6 Unscheduled Visit (if needed)

Unscheduled visits may occur at any time during this study. Labs may be drawn at PI discretion. Any of the following activities may be performed:

- Obtain interim medical history, including an assessment for new medical conditions by interview of subjects and note any changes since the previous clinic visit or phone call.
- Ask about febrile/rash illness. If the subject reports history of febrile illness and either non-purulent conjunctivitis or arthralgia within the past 14 days, conduct a febrile/rash illness Assessment and sample collection as per [Section 8.7](#).
- Record concomitant medications on the appropriate case report form if  $\leq$  Day 29 after last study vaccination.
- Obtain vital signs including oral temperature, blood pressure, and pulse if visit occurs on or before Day 57.
- Perform a targeted physical examination, if indicated based on review of complete medical history.
- Examine vaccination site for local reactions if visit occurs  $\leq$  28 days after first or 2nd vaccination.
- Review memory aid if visit occurs  $\leq$  8 days after 1st or 2nd vaccination.
- Obtain labs (safety, immunity (cellular and humoral) and systems biology) appropriate to that visit if visit occurs within window of a regular study visit.
- Collect urine for urine dipstick for glucose and protein if indicated as part of the safety laboratory tests.
- Assess for AEs if occurs on or prior to Day 57.
- Assess for unsolicited SAEs and AESIs and new onset chronic medical conditions and record on the appropriate case report form.
- May obtain urine for pregnancy if subject is a female of child bearing age and visit occurs on or before Day 57.

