Screening laboratory tests, including WBC, hemoglobin, hematocrit, platelet count, ALT, AST, bilirubin, BUN, and creatinine, may be repeated once on a second screening visit if test is out of acceptable range, provided there is an alternative explanation for the out of range value; All screening tests need to be done within 28 days of Day 1, otherwise all tests, except for serology for HIV 1/2, Hepatitis C virus, or Hepatitis B surface antigen, will need to be repeated within the screening period. Safety laboratories include WBC, hemoglobin, hematocrit, platelet count, ALT, AST, bilirubin, BUN, and creatinine.

Distribute memory aid to subjects and give them study materials.

Assess vaccination site.

If visit occurs  $\leq$ 8 days after 1st or 2nd vaccination. Includes local and systemic reactogenicity assessment

If prior to  $\leq$ 28 days after the last study vaccination.

If visit occurs  $\leq$ 15 days after 1st or 2nd vaccination.

If visit occurs on or prior to Day 57.

Obtained prior to vaccination.

If visit occurs within window of a study Day when these labs would be collected.

Part of the plasma from the CPT tubes will be saved for systems biology.

Baseline serology will include testing for DENV and ZIKV. AFI/ARI assessment will include testing for DENV, ZIKV, and CHIKV.

If the subject reports history of AFI or ARI within the past 14 days at any time after signing the ICF, conduct an AFI/ARI assessment and sample collection as per [Section 8.7](#),

PBMCs for HLA typing only on Day 1.

Assess for SAEs and AESIs from time of first ZPIV administration until end of study.

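### The febrile/rash trigger at the early-termination and unscheduled visits omits rash and the two-day fever requirement, contradicting the protocol's own AFI/ARI rules

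*Protocol*

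**What the plan says.** Protocol 7.1.3 sets the surveillance case definitions. For fever, "AFI will be defined as grade 1 or higher fever lasting at least two consecutive days and accompanied by any one of" new rash away from the vaccination site, arthralgia or nonpurulent conjunctivitis. For rash, "ARI will be defined as new rash not limited to vaccination site", with no fever needed. The same section gives the rule for acting on a report: "The following assessment will be completed if a report of AFI or ARI is made during a regular or unscheduled visit".

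The scheduled visits after screening use these defined terms. At the final visit (8.4.1) the instruction reads "If the subject reports history of AFI/ARI within the past 14 days, conduct a febrile/rash illness assessment and sample collection". Appendix A footnote 20 states the condition generally, "If the subject reports history of AFI or ARI within the past 14 days at any time after signing the ICF", and sends the subject to 8.7.

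Sections 8.5 and 8.6 differ. Both tell staff to ask about febrile or rash illness, but then set a narrower condition for acting on the answer. In 8.5 it is: "If the subject reports history of febrile illness and either non-purulent conjunctivitis or arthralgia within the past 14 days, conduct a febrile/rash illness Assessment". In 8.6 the condition is again "history of febrile illness and either non-purulent conjunctivitis or arthralgia within the past 14 days". The list in 8.5 is mandatory. The list in 8.6 is permissive: "Any of the following activities may be performed".

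**The concern.** Rash appears in the question that staff ask but not in the condition that leads to assessment and sampling. A coordinator working from the 8.5 checklist could record a new rash and, following the text, stop there. The condition is also too wide in one respect: it does not require fever on two consecutive days, so a one-day fever with arthralgia would be assessed although it is not an AFI.

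What is at stake is the exploratory surveillance objective: the incidence of ZIKV and DENV infection up to each subject's last visit, and the two exploratory endpoints built on AFI and ARI (Protocol 3.1.3 and 3.2.3). A qualifying illness that is not sampled within 14 days loses the acute route to laboratory confirmation. If staff applied 8.5 literally, subjects who leave early would have their last 14 days checked under a narrower rule than subjects who reach Visit 23.

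**Working it through.** The plan states no figure to reproduce. The check compares the case definition with the trigger and then sets the governing passages side by side.

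**1. Symptom patterns.** Four signs matter: fever (F), rash (R), arthralgia (A) and nonpurulent conjunctivitis (C). Each is present or absent, giving 2^4 = 16 patterns. Fever duration is ignored here because 8.5 and 8.6 do not state it.

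- Definition (7.1.3): AFI = F and (R or A or C); ARI = R.
- Trigger (8.5, 8.6): F and (A or C).

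Patterns meeting AFI or ARI: rash present, 8; rash absent but fever with A, C or both, 3. Total 8 + 3 = 11.

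Patterns meeting the trigger: fever present, rash present or absent (2), and A, C or both (3), so 2 × 3 = 6. All 6 are among the 11.

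Missed: 11 − 6 = 5.

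| Missed pattern | Count | Qualifies as |
|---|---|---|
| Rash, no fever (alone, +A, +C, +A+C) | 4 | ARI |
| Fever + rash, no A, no C | 1 | AFI and ARI |

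Fever plus rash with arthralgia or conjunctivitis is still caught. With the AFI/ARI wording, all 11 of 11 would be caught.

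**2. Which other passages reach each visit.**

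| Passage | Unscheduled (8.6) | Early termination (8.5) |
|---|---|---|
| 7.1.1, reported AFI/ARI within 14 days is evaluated per 8.7 | yes, as a follow-up visit | yes, as a follow-up visit |
| 7.1.3, assessment rule | named | not named |
| 8.7, illness visit | named (a type of unscheduled visit) | not named |
| Appendix A footnote 20 | yes, by its general wording | yes, by its general wording |
| The visit's own list | permissive, rash omitted | mandatory, rash omitted |

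**3. What can be recovered later.** The titer-rise route in Protocol 3.2.3 needs a sample from a visit after the illness. A continuing subject seen under 8.6 will have later visits. A subject leaving under 8.5 will not, and 8.5 draws humoral samples only if the visit falls in the window of a regular one. For a recent rash at early termination, the acute sample may be the only route to confirmation.

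**4. How the SAP would show an unsampled case.** The shells for Tables 147, 154, 168 and 182 offer PCR positive, titer-rise positive, any positive, and negative laboratory confirmation. There is no untested row, so an unsampled rash illness could be counted as negative.

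**The case against.** The strongest reply is that the rest of the protocol already requires the right action. Sections 7.1.1, 7.1.3 and 8.7 and footnote 20 all call for assessment of AFI and ARI, and 7.1.3 has subjects asked about both at every follow-up visit. The 8.5 condition says when to assess; it does not forbid assessment otherwise. This stands. A reader might infer that rash illness goes unassessed at these visits. The documents do not support that: they show a contradiction that could lead to missed sampling, not an established gap. For 8.6 the reply is nearly complete, since its list is optional and 7.1.3 and 8.7 name unscheduled visits. For the same reason, ascertainment that differs by withdrawal status is a possibility that depends on literal use of 8.5, not a demonstrated bias.

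A reader might also try to size the problem from withdrawals. An assumed 10–20% of 90 gives 9–18 subjects, but that counts leavers, not missed cases. An affected subject must leave, have had a missed-pattern rash in the previous 14 days, not have reported it under the three-day request, attend in person, and meet staff who follow 8.5 over 7.1.1 and footnote 20. Early-termination visits may be refused (5.3.3) or held by telephone (5.3.1), where no sample is possible under any wording. The affected number could be zero.

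Timing is a further objection. SAP 6.2 dates the combined interim analysis 22 December 2020, and its third component required every subject to have completed one year after the second vaccination. From Day 388 to Day 750 is 362 days. If the interim followed its stated trigger, the last visits fell around December 2021 to January 2022, before this protocol's date of 19 September 2022. New wording may therefore reach no visit. This too stands, and it shifts the weight of the fix to the record review.

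**Conclusion.** The trigger in 8.5 and 8.6 is inconsistent with the protocol's own definitions and with four other provisions (7.1.1, 7.1.3, 8.7 and footnote 20), and the passages must be reconciled. Taken literally, it misses 5 of 11 qualifying symptom patterns and admits one-day fevers that are not AFI. The second error costs only extra sampling, provided the AFI definition is applied at analysis.

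The practical risk is concentrated at early termination. There, 7.1.1 and footnote 20 stand against an explicit, mandatory, visit-specific instruction, and a missed sample cannot be replaced by a later titer. The pattern count gives no weight to how common each pattern is and says nothing about how many subjects were affected. No sample size, error rate or primary or secondary endpoint depends on this point.

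**What to change.** In 8.5 and 8.6, replace the condition with the trigger already used at the scheduled visits, a history of AFI/ARI within the past 14 days, leading to assessment and sampling under 8.7. Name early termination in 7.1.3 and 8.7 so that all the passages agree. This takes a few sentences of existing wording; the assessment, assays and forms already exist.

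For early-termination and unscheduled visits already held, review the records for rash meeting the 7.1.3 definition and count those events as ARI or AFI. Add a not-tested row to SAP Tables 147, 154, 168 and 182 and their subgroup versions. Report an event with no acute sample there, not under negative laboratory confirmation; where a pair of flanking sera exists, show its titer result alongside. The review covers a limited set of visits among about 90 subjects. It can correct the AFI/ARI counts and show what was not tested, but it cannot recover acute samples that were never drawn.
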